**Retrospective Evaluation of the Efficacy and Safety of Micronized Adipose Tissue
Obtained with the Matrigen Device in the Treatment of Patients with Interstitial
Cystitis**

04/04/2025

1. Introduction and Rationale

Interstitial cystitis (IC) is a chronic, multifactorial urological condition characterized by bladder pain, pressure, and persistent urinary symptoms. Its complex and not yet fully understood pathophysiology involves autoimmune mechanisms, dysfunction of the urothelial barrier, alterations in sensory neural pathways, muscle abnormalities, and degradation of subepithelial connective tissue. Epidemiological data show a significant prevalence, often affecting adults of working age and disproportionately impacting women, with a major effect on quality of life. Conventional treatments (including behavioral modifications, pharmacotherapy, and invasive procedures) frequently fail to provide lasting relief, underscoring the need for alternative therapeutic strategies. Regenerative medicine has emerged as a promising field capable of targeting the underlying pathophysiology of chronic diseases. Among its tools, mesenchymal stromal cells (MSCs) derived from adipose tissue are of particular interest due to their availability, regenerative potential, and immunomodulatory properties. Through paracrine signaling, secretion of trophic factors, soluble mediators, and exosomes, MSCs may support tissue repair and reduce inflammation. Micronized adipose tissue (MAT), obtained through minimal manipulation using intraoperative techniques, provides a scaffold-rich environment that preserves stromal cell integrity and enhances therapeutic potential. The Matrigen device allows the processing of autologous fat into MAT that meets the European Regulation (EC) No. 1394/2007 criteria for “non-substantial manipulation.” Preclinical and early clinical studies have highlighted the potential of adipose-derived MSCs in treating IC/bladder pain syndrome (Wen et al., 2021; Dayem et al., 2022) and urinary incontinence (Garcia-Arranz et al., 2019), showing both regenerative and anti-inflammatory effects.

2. Objective

To retrospectively evaluate the safety and effectiveness of micronized adipose tissue obtained with the Matrigen device in improving symptoms and urodynamic outcomes in patients previously treated for interstitial cystitis at our institution.

3. Study Design

This is a **retrospective observational cohort study** involving **20 adult patients** diagnosed with interstitial cystitis, treated between 04 April 2024 and 08 October 2024 at our center with intraoperative infiltration of micronized adipose tissue obtained using the Matrigen system. Clinical, procedural, and follow-up data were collected from electronic medical records and anonymized prior to analysis.

4. Endpoints

Primary Endpoints

- Urodynamic testing results at baseline and 6 months post-treatment
- Cystoscopic findings at baseline and 6 months post-treatment

Secondary Endpoints

- Patient-reported pain and symptom scores using VAS, GLOBE SF-36, O’Leary IC Symptom/Problem Index, and MOS Sexual Functioning Scale at baseline and 1, 2, and 3 months post-treatment
- Physical examination at baseline and 3 months post-treatment

- Evaluation of bladder capacity, detrusor pressure, compliance, urinary flow, and post-void residual volume at baseline and 6 months
- Cystoscopic evaluation of mucosal condition and lesion status at baseline and 6 months

5. Inclusion Criteria

- Adult patients (≥ 18 years) diagnosed with interstitial cystitis
- History of treatment with micronized adipose tissue using the Matrigen device
- Complete clinical documentation, including surgical and follow-up data
- Informed consent previously obtained for data use in clinical research

6. Exclusion Criteria

- Active urinary tract infections at time of treatment
- Corticosteroid therapy within 3 months prior to the intervention
- History of tuberculosis, malignancy, or severe systemic disease
- Pregnancy or lactation at the time of the procedure

7. Clinical Procedures

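### Safety is a stated aim in the title and objective, but no endpoint names an adverse event, complication, donor-site event or re-intervention, so the protocol supports at most a limited safety statement

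*Protocol*

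**What the plan says.** The title announces a "Retrospective Evaluation of the Efficacy and Safety of Micronized Adipose Tissue". Section 2 sets the aim: "To retrospectively evaluate the safety and effectiveness of micronized adipose tissue obtained with the Matrigen device in improving symptoms and urodynamic outcomes".

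Section 4 has two primary endpoints, urodynamic testing and cystoscopic findings, each at baseline and month 6. The secondary endpoints are:

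- scores completed by the patients on several instruments, where the last two instruments and the schedule read "O’Leary IC Symptom/Problem Index, and MOS Sexual Functioning Scale at baseline and 1, 2, and 3 months post-treatment";
- one clinical check, given without further detail as "Physical examination at baseline and 3 months post-treatment";
- the parts of the urodynamic test, among them post-void residual, again at month 6;
- the parts of the cystoscopy, worded as "Cystoscopic evaluation of mucosal condition and lesion status at baseline and 6 months".

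On data, Section 3 states: "Clinical, procedural, and follow-up data were collected from electronic medical records and anonymized prior to analysis". Section 5 admits only patients with "Complete clinical documentation, including surgical and follow-up data". Section 7 describes two invasive steps in one session: a fat harvest of about 50 mL from the abdomen or proximal thigh (7.1), and multiple injections into the bladder wall during urethrocystoscopy (7.2).

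**The concern.** The objective has two parts, safety and effectiveness. Section 4 supplies outcomes for effectiveness and assigns none to safety. A safety conclusion drawn from the endpoints as listed could rest only on whether effectiveness measures worsened at a few fixed visits.

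That is weak evidence for a procedure with two operative sites. A complication that arises soon after the session and resolves before the next scheduled assessment need not leave a trace in any listed endpoint. A re-intervention between visits is not recorded by a score or an examination at a fixed time. A report could then state that the treatment was safe although no endpoint had counted events.

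**Working it through.** The protocol states no safety figure, so there is nothing to reproduce. The check compares the stated aim with the endpoints, and then asks what an event count in this cohort could show.

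**Step 1. Endpoints against the safety aim (Section 4).**

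| Assessment | Post-treatment time | Names an event? | Possible safety information |
|---|---|---|---|
| Patient-reported scores | Months 1, 2, 3 | No | Worse pain or symptoms at those times |
| Physical examination | Month 3 | No | Findings present at month 3; body region not specified |
| Urodynamics (primary bullet plus the component bullet) | Month 6 | No | Post-void residual and other function at month 6 |
| Cystoscopy (primary bullet plus the component bullet) | Month 6 | No | Mucosal condition and lesions at month 6 |

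The six bullets reduce to four assessments because the last two secondary bullets spell out the two primaries (6 − 2 = 4). Of the six, 0 name an adverse event, complication, donor-site event or re-intervention. The remaining sections (3 and 5 to 8) do not name one as an outcome either.

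**Step 2. Timing.** The first scheduled assessment of any kind is the month 1 scores. The first physical examination after treatment is at month 3, and the first look at the bladder is at month 6. The interval from the procedure to month 1 has no endpoint.

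**Step 3. What an added event endpoint could show.** The input is n = 20 (Section 3). With 0 events, the upper limit of the exact two-sided 95% interval is 1 − 0.025^(1/n) = 1 − 0.025^(1/20) = 0.168, or 16.8%. The chance of seeing at least one event is 1 − (1 − p)^20. The protocol gives no event rate, so p is an assumption:

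- p = 1%: 18%
- p = 2%: 33%
- p = 5%: 64%
- p = 10%: 88%

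These figures describe the precision available after the fix. They would be the same for any binary outcome in 20 patients, so they do not measure the defect. Its measure is the count in Step 1.

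**Step 4. Denominator.** Section 5 selects on complete surgical and follow-up documentation. If m treated patients were left out on that ground and x of them had an event, 0/20 becomes x/(20 + m). Patients with a complicated course or lost follow-up are plausible members of that group, so a rate among the 20 may be too low even if their own records are perfect. The protocol does not give m.

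**The case against.** The strongest defence has three parts.

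*The listed measures already carry safety information.* Section 2 can be read as judging the treatment through symptoms and urodynamics, and worsening on any listed measure would be a harm. This stands in part. Scores, examination, post-void residual and cystoscopy can show persistent harm, so it would be wrong to infer that the study has no safety information. They still do not record transient events or re-interventions.

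*The detail belongs to the SAP.* The event list, abstraction window and interval method are often set there, and the SAP is not at hand. A reader might infer that no list or window has been fixed anywhere, or that no event-based result can emerge. The protocol alone does not support that: Section 3 says procedural and follow-up data were collected, so event data may already be held. The remaining point is narrower. The outcome that answers a stated objective belongs in the protocol's endpoint section, and this one has such a section and assigns safety nothing in it.

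*The donor site is covered.* A reader might infer that harvest-site events fall wholly outside the endpoints. They do not, because the month 3 examination is not restricted by body region and could find a problem still present then. What the text supports is that no endpoint names the donor site and that earlier, resolved events there would probably be missed.

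**Conclusion.** The point holds as a mismatch between objective and endpoints within one document. Safety is named in two places (title and Section 2), and 0 of 6 endpoint bullets name a safety event. As written, the protocol supports at most a limited safety statement: whether the listed measures worsened at months 1 to 3 and month 6. It should be fixed. The effectiveness endpoints are unaffected.

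The conclusion rests on the protocol text alone and does not depend on the precision figures. It assumes only that some procedural events can occur and resolve between scheduled assessments. It is not evidence that the treatment is unsafe, or that events went unrecorded in the charts.

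**What to change.** Add a safety endpoint to Section 4: adverse events related to the procedure, the bladder or the donor site, and re-interventions, abstracted from the existing records from the procedure to 6 months. Because Section 3 describes data collection as already done, label the endpoint as added after data collection.

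Report counts and proportions with exact 95% intervals. Use as denominator all patients treated with the device in the Section 3 window, or report how many were excluded for incomplete documentation under Section 5 and why. State that ascertainment is limited to routine records, so that an upper limit such as 16.8% for 0 of 20 is not read as firmer than it is.

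If events cannot be abstracted, limit the safety claim in the title, objective and conclusions to the presence or absence of worsening on the listed examination, post-void residual and cystoscopic measures, or remove it.

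The cost is a modest chart review for 20 patients, somewhat more if the denominator is widened. Since the data were anonymized, it may mean returning to identifiable records. The endpoint will still miss what was never written down. Narrowing or removing the claim costs almost nothing.

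### Does stopping the symptom scores at month 3, when the primary endpoints are read at month 6, call for a change to the protocol?

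*Protocol*

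**What the plan says.** Section 4 (Endpoints) gives a time point for every endpoint. The two primary endpoints are "Urodynamic testing results at baseline and 6 months post-treatment" and "Cystoscopic findings at baseline and 6 months post-treatment". Among the secondary endpoints, one line holds the four patient-reported instruments (VAS, GLOBE SF-36, the O'Leary index and the MOS scale) and ends "MOS Sexual Functioning Scale at baseline and 1, 2, and 3 months post-treatment". The next is "Physical examination at baseline and 3 months post-treatment". The last two return to the bladder: "Evaluation of bladder capacity, detrusor pressure, compliance, urinary flow, and post-void residual volume at baseline and 6 months" and "Cystoscopic evaluation of mucosal condition and lesion status at baseline and 6 months".

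Section 2 (Objective) asks about safety and about effectiveness on symptoms and on urodynamics, without a time horizon for either. Section 3 (Study Design) describes a retrospective cohort of 20 patients treated from 04 April to 08 October 2024, and says that the "follow-up data were collected from electronic medical records and anonymized prior to analysis". Section 5 (Inclusion Criteria) requires "Complete clinical documentation, including surgical and follow-up data" but does not name the items that make a record complete.

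**The concern.** Section 1 describes interstitial cystitis by pain, pressure and urinary complaints, and justifies a new treatment partly because relief from existing ones often does not last. Symptoms are also named in the objective. One would therefore expect at least one symptom score at the visit where the primary endpoints are read.

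As scheduled, the study can describe symptoms up to month 3 and the bladder at month 6, but it cannot relate the two at the same post-treatment time. If symptoms returned after month 3, no scheduled score would record it. The practical risk is that an improvement in urodynamics or cystoscopy at month 6 is read as patient benefit at month 6, which the scheduled symptom data could neither confirm nor refute.

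**Working it through.** The Protocol contains no calculation on this point to reproduce. The check sets the schedule out and asks what could follow from it.

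**1. Post-treatment time points (Section 4).**

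| Domain | Status | Months |
|---|---|---|
| Urodynamics | primary, detailed again as secondary | 6 |
| Cystoscopy | primary, detailed again as secondary | 6 |
| Patient-reported scores | secondary | 1, 2, 3 |
| Physical examination | secondary | 3 |

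The sets {1, 2, 3} and {6} share no element, and the shortest lag is 6 − 3 = 3 months. No other section adds a symptom score at month 6. The month-6 urodynamic measures are functional tests and do not stand in for one.

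**2. Which figures carry information.** Counting lines gives 4 of 6 endpoints at month 6 only, but the two secondary bladder lines cover the same assessments at the same times as the two primary ones. By domain it is two at month 6 and two ending at month 3. Counting scores gives 4 instruments × 3 visits × 20 patients = 240, with none at month 6, but that is true by construction. The 3-month lag is the one informative number.

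**3. Does the schedule contradict anything?** The objective has two effectiveness parts. Symptoms have a baseline and three later scores; urodynamics have a baseline and one later assessment. Each part can be answered over its own period. No section announces a durability conclusion for symptoms, a 6-month symptom claim, or a correlation of symptom change with bladder change. The remark on relief that does not last concerns conventional treatments; it is not an endpoint.

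**4. Would a return of symptoms be invisible?** Not necessarily. Section 3 says that clinical and follow-up data came from the medical records, so a relapse noted in the chart might be found. What is supported is narrower: no scheduled score would capture it.

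**5. What could still be changed?** The Protocol is dated 04/04/2025. Six months after the first treatment date is 04 October 2024; six months after the last is 08 April 2025, 4 days after the Protocol's date. So the nominal month-6 date had passed for everyone except any patient treated after 04 October 2024, and Section 3 already speaks of the data in the past tense. Two options remain:

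- *Extract any symptom score recorded near month 6.* The Protocol does not say that such scores exist, so the number available could be anywhere from 0 to 20. Scores outside the schedule may come mainly from patients who returned with complaints, and linking them to anonymized data may not be possible. A window fixed before anyone has seen the scores may also be unattainable.
- *Add a limitation sentence.* This is always feasible, but it alters no endpoint, time point, analysis or number.

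**The case for a change.** The strongest argument for acting is that the cost is trivial (one extraction item for 20 records, or one sentence) while the misreading it prevents is plausible. Symptoms are half of the effectiveness question, the Protocol's own rationale appeals to lasting effect, and nothing in the text warns against carrying a month-6 bladder result over to month-6 symptoms. Nor can the point be left to an analysis plan, because the assessment schedule is fixed in the Protocol.

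Much of this stands. The gap is real, the schedule does belong to the Protocol, and the inference from bladder findings to symptoms at month 6 would be unsupported. What does not stand is the step from there to a correction. Primary and secondary endpoints may have different time points, and in a retrospective study the schedule may simply reflect what was routinely recorded. Section 4 states every time point, so any reader can see where the symptom data end. The extraction would at best give an incomplete and possibly selective set of scores, usable only descriptively. The sentence concerns how results are worded, which is the business of the report.

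**Conclusion.** No change to the plan. The observation is correct: the last scheduled symptom score precedes the primary assessment by 3 months. That limits what may be concluded; it is not a wrong rule, a wrong figure or a contradiction. The Protocol gives no relapse rate, so the size of any symptom change after month 3 is unknown, and no sample size or error rate depends on the point.

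This rests on two assumptions: that the data are fixed as Section 3 describes, and that the report claims no more than the schedule supports. Analysts would ordinarily meet the second by confining symptom conclusions to the first 3 months and by not presenting a month-6 bladder improvement as evidence of month-6 symptom benefit. If the records happen to hold linkable symptom scores near month 6, they can be reported descriptively, with the number available and a caution about selective recording. None of this requires an amendment. The judgement would differ if the study were prospective with visits still to come, or if the Protocol claimed symptom benefit at 6 months.

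### Section 6 excludes from among patients who have already received MAT, although safety is an objective, and its third criterion has no reference date

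*Protocol*

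**What the plan says.** Protocol Section 2 states the objective: "To retrospectively evaluate the safety and effectiveness of micronized adipose tissue", in patients whom the institution has already treated. The title also names safety. Section 3 describes a "retrospective observational cohort study involving 20 adult patients", all "treated between 04 April 2024 and 08 October 2024 at our center". The Protocol is dated 04/04/2025.

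Section 5 makes exposure a condition of entry: "History of treatment with micronized adipose tissue using the Matrigen device". It also requires earlier consent to research use of the data.

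Section 6 lists four exclusions:

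- The first concerns infection and is dated to the procedure: "Active urinary tract infections at time of treatment".
- The second concerns steroid use in the three months before the procedure.
- The third carries no date: "History of tuberculosis, malignancy, or severe systemic disease".
- The fourth concerns women who were pregnant or breastfeeding when treated.

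The Protocol gives no total of patients treated in the window and no number excluded. It does not say whether these four conditions were also applied when patients were selected for the procedure.

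**The concern.** In a prospective trial, criteria of this kind keep people from being exposed. Here the exposure has already happened, so as rules for selecting records they can only take exposed patients out of the denominator. For effectiveness that is an ordinary restriction of the population. For safety, the natural group is everyone who received the treatment, and a complication in a treated but excluded patient would not appear in the report.

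The third criterion raises a further problem. Records are being selected after treatment, and the criterion sets no date by which the condition must have been present. A diagnosis made after the injection could count as grounds for exclusion, although a new malignancy or serious systemic illness after a procedure is something a safety evaluation should capture. The severity of a systemic disease is also left undefined, so the reviewer of the record has to judge it.

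**Working it through.** **Order of events.** The last treatment date is 08 October 2024 (Section 3) and the Protocol date is 04/04/2025. The interval is 23 + 30 + 31 + 31 + 28 + 31 + 4 = 178 days. As criteria of this Protocol, the exclusions therefore apply only to patients already treated. The inclusion criterion on exposure confirms this.

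**Reference dates in Section 6.**

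| Exclusion | Tied to the procedure? |
|---|---|
| Urinary tract infection | Yes, at treatment |
| Corticosteroids | Yes, the 3 months before |
| Tuberculosis, malignancy, severe systemic disease | No date given |
| Pregnancy or lactation | Yes, at the procedure |

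Three of the four can be settled from status at or before the procedure. The third cannot, as written. The word history does not settle it. Section 5 uses the same word for the MAT treatment itself, and there it can only look back from the time of record selection. Read the same way in Section 6, it would cover conditions that arose after MAT.

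**Size.** The Protocol gives no event rate or exclusion count, so there is no figure to reproduce. The following is illustration only. Assume 0 events among the 20 retained patients, m treated patients excluded, and x events among those m. The rate in all exposed patients is x/(20 + m). With n = 20 + m, the exact (Clopper-Pearson) two-sided 95% limits are:

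- x = 0: lower limit 0, upper limit 1 − 0.025^(1/n). For n = 20 this is 1 − 0.025^(1/20) = 16.8%.
- x ≥ 1: lower limit is the 0.025 quantile of Beta(x, n − x + 1); upper limit is the 0.975 quantile of Beta(x + 1, n − x).

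| Excluded m (assumed) | Events x among them (assumed) | Rate in all exposed | 95% limits |
|---|---|---|---|
| 0 | 0 | 0/20 = 0% | 0 to 16.8% |
| 1 | 1 | 1/21 = 4.8% | 0.1 to 23.8% |
| 2 | 0 | 0/22 = 0% | 0 to 15.4% |
| 2 | 1 | 1/22 = 4.5% | 0.1 to 22.8% |
| 2 | 2 | 2/22 = 9.1% | 1.1 to 29.2% |
| 5 | 2 | 2/25 = 8.0% | 1.0 to 26.0% |
| 10 | 1 | 1/30 = 3.3% | 0.1 to 17.2% |
| 10 | 2 | 2/30 = 6.7% | 0.8 to 22.1% |

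Over these assumptions, one or two unreported events move the observed rate from 0% to between about 3% and 9%. With no events among the excluded, the rate stays at 0% and the upper limit falls slightly.

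**The case against.** The strongest reply is that nobody may have been dropped. The criteria could repeat the conditions under which the procedure was offered, and the wording of the three dated ones fits that reading. This stands: nothing in the Protocol shows that any treated patient met an exclusion. A reader might infer that exposed patients were in fact removed, but the text supports only that they could be. The Protocol does not say which case applies.

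A reader might also infer that the excluded patients are those at highest risk of harm. The Protocol gives no risk by infection, steroid use, malignancy or pregnancy, so that inference has no support in it.

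Thirdly, restricting a cohort on status at or before the procedure narrows the population to which the result applies. It does not by itself bias the estimate within that population. This also stands, for the three dated criteria. It does not cover the third, where the missing date could let post-treatment information decide eligibility.

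Fourthly, the illustrative counts are assumed and the intervals overlap heavily. That is correct. They show how much a single event matters with about 20 patients and are not an estimate of bias.

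Finally, analysis sets and exclusion tables are often left to the statistical analysis plan, which is not at hand. Their absence alone is no fault. Eligibility, however, is fixed in this Protocol, and an analysis plan could not bring back patients whom Section 6 keeps out of the study.

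**Conclusion.** The point holds in a limited form. As written, Section 6 can leave exposed patients out of a study with a safety objective, and its third exclusion could absorb a possible safety outcome because it has no reference date. Whether either has happened cannot be told from the Protocol.

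The size is therefore unknown. It is nil if the criteria also governed who was treated and the third was judged on status before the procedure. Otherwise, under the assumed counts above, one missed event is enough to change a report of no complications into a report of some. The point does not establish that the safety result is biased. It is worth acting on because the correction is cheap and a reader of the results could not otherwise tell which case applies.

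**What to change.** - Report safety for all interstitial cystitis patients given MAT with the device at the centre from 04 April to 08 October 2024 whose consent allows data use. Apply Section 6 only to the effectiveness analysis.
- Tie the third exclusion to status documented before the procedure, and say what counts as severe systemic disease.
- State whether the Section 6 criteria also governed who was treated, or only which records were selected.
- Report the number treated in the window and the number each criterion removes.

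The cost is a review of a few more existing records and one flow table. The complication rate may turn out less favourable. Two neighbouring matters need their own attention: Section 4 lists no explicit adverse-event endpoint, so what is to be counted in the wider group must be defined; and the Section 5 requirement of complete documentation is a separate selection that should not be carried into the safety group unnoticed.
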